6.3.3 Safety Analysis

All subjects entered into the study will be included in the safety analysis. The frequencies of AEs by type, body system, severity and relationship to study arm will be summarized. SAEs (if any) will be described in detail.

6.4 Sample Size and Power

No preliminary data about incidence of IH in infants with moderate or severe BPD are available. Therefore, our sample size is based on extrapolations from the existing studies. Rhein reported 8.2 +/- 11.5 events of 5 seconds or longer per hour (197 per day) at 36 weeks PMA.(8) Poets reported a median 88.4 events of 10 seconds or longer per day in the Canadian Oxygen Trial.(7) We assume that fewer than half of these will be longer events that meet our study definition of IH, and estimate that our study participants will have between 20-30 IH events per 8-hour period at baseline. We plan to recruit 42 participants with useable data, which will provide sufficient power to detect a relative reduction of 30% between the high and low SpO₂ target groups if the baseline rate is 30 events per 8 hours. Therefore, our target sample size is 42 children *with complete data*.

Mean weight at 36 weeks PMA based on the Olsen growth curves is 2.8 kg,(14) and mean weight at 6 months CA based on the WHO growth curves is 7.9 kg.(15) Therefore, we assume a mean growth of 5.1 kg in the higher SpO₂ group and less weight gain in the lower SpO₂ group. The target sample size of 42 children will provide >80% power to detect a mean difference in growth of 0.5kg between the two study groups.

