Secondary analyses of a large randomized trial comparing higher versus lower SpO₂ targeting for newborn extremely preterm infants (6) demonstrated that IH, and in particular events <80% for at least one minute, are common in this population between birth and at least 9-10 weeks of age. (7) The duration of time with SpO₂ <80% is associated with the combined outcome of death after 36 weeks or disability at 18 months, cognitive or language delay, motor impairment, and severe retinopathy of prematurity. Importantly, this effect is significantly stronger when IH occurs 9- 10 weeks after birth than when it occurs earlier. While the neonatal community has been striving to minimize events in the weeks prior to discharge, these data force us to evaluate the value of reducing IH throughout infancy. It is unknown whether infants with BPD continue to have IH after 36 weeks PMA or after hospital discharge, or whether ameliorating this with longer-term use of supplemental oxygen would improve outcomes of these high-risk infants. IH is an important and novel therapeutic target in BPD, and may be a key component of decisions regarding safe and appropriate use and weaning of supplemental oxygen.

A recent trial of late caffeine therapy enrolled infants who were at least 33 PMA and in room air. (8) The control group had an average of 8.4 episodes of intermittent hypoxemia (decline in SpO₂ by at least 5% from baseline to <90% and lasting at least 5 seconds) per hour at 35 weeks PMA, which declined to 3.0 events per hour at 39 weeks PMA. The total time spent with saturations <90%, <85%, and <80% declined dramatically between 35 and 39 weeks. The clinical relevance of these more minor IH episodes and periods of hypoxia have not yet been demonstrated.

Our study collaborators have developed a simple, low-cost device for the BPD STAR Trial that securely transmits oximetry data wirelessly from the home environment. This device will enable us to implement a novel approach to studying management and outcomes of BPD. This study will provide critical data about whether infants with BPD continue to have IH after discharge; whether targeting higher SpO₂ ameliorates IH; and whether this management strategy is associated with improved outcomes until 6 months of age.

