3.4.1 Inclusion Criteria

- 1) Patient at CHOP,HUP, PAH (including both inborn and outborn infants)
- 2) Pre-term males or females infants born at <30 0/7 weeks gestation
- 3) Current age 34 0/7 to 43 6/7 weeks postmenstrual age
- 4) Diagnosis of moderate or severe Bronchopulmonary Dysplasia (as above)
- 5) Infant has never been discharged to home from the hospital

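### Section 6.4's planning rate of 20-30 IH events per 8 hours fits only the caffeine trial's 36-week figure; the section's other source and the 39-week figure in section 1.3 give lower ceilings, and the SD behind the power claim is not stated

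*Combined protocol and SAP*

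**What the plan says.** Section 6.4 states that no IH data exist for infants with moderate or severe BPD and that the sample size is extrapolated from other studies. It cites two. The late-caffeine trial is quoted as "8.2 +/- 11.5 events of 5 seconds or longer per hour (197 per day) at 36 weeks PMA", and the second source as "a median 88.4 events of 10 seconds or longer per day in the Canadian Oxygen Trial". One discount is applied to both: "We assume that fewer than half of these will be longer events that meet our study definition of IH". The result is that the investigators "estimate that our study participants will have between 20-30 IH events per 8-hour period at baseline". Adequate power for a 30% relative reduction with 42 evaluable infants is then asserted on condition that the rate is 30, the top of that range. No SD, alpha, sidedness or numerical power is given for the IH calculation.

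Section 1.3 describes the same caffeine trial further. Its control group had 8.4 events per hour at 35 weeks PMA, "which declined to 3.0 events per hour at 39 weeks PMA". Section 6.4 does not use this decline.

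Infants may enter at "Current age 34 0/7 to 43 6/7 weeks postmenstrual age" (section 3.4.1). Section 5.2.1 names the IH comparisons at 40 weeks PMA, 3 months CA and 6 months CA. The primary objective in section 2.1 runs from 36 weeks PMA to 6 months CA.

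**The concern.** The discount rule and the two sources should lead to the planning range, and for one of the two sources they do not. The rate that does fit was measured at 36 weeks, whereas the first named IH comparison is at 40 weeks, and the protocol's own background shows the rate falling steeply between 35 and 39 weeks.

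The discount may also be generous. Section 6.4 justifies it by duration alone. The caffeine-trial events were also shallower: a fall of at least 5% to below 90% for 5 seconds or more, against below 80% for 30 seconds or more in this study.

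At stake is the sample-size statement for a primary endpoint. If the rate at the compared ages is well under 30, a 30% relative reduction is a much smaller absolute difference. Without a stated SD, nobody can tell whether 42 infants could detect it.

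**Working it through.** **1. Source rates on the 8-hour scale, with the discount applied.** Events per hour are multiplied by 8 and events per day divided by 3. Half of the result is the ceiling under the rule.

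| Source | Per 8 h | Ceiling | Share needed to reach 20-30 |
|---|---|---|---|
| Caffeine trial, 35 weeks (section 1.3) | 8.4 × 8 = 67.2 | <33.6 | 30-45% |
| Caffeine trial, 36 weeks (section 6.4) | 8.2 × 8 = 65.6 | <32.8 | 30-46% |
| Canadian Oxygen Trial, median (section 6.4) | 88.4 / 3 = 29.5 | <14.7 | 68-102% |
| Caffeine trial, 39 weeks (section 1.3) | 3.0 × 8 = 24 | <12 | 83-125% |

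The plan's range is therefore reachable from the 36-week rate (and from the 35-week rate in section 1.3). It breaks the under-half rule for the second source cited in 6.4 and for the 39-week rate. The fall from 8.4 to 3.0 is (8.4 − 3.0) / 8.4 = 64%.

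**2. Absolute size of a 30% reduction.** 0.30 × 30 = 9.0 events; 0.30 × 20 = 6.0; 0.30 × 14.7 = 4.4; 0.30 × 12 = 3.6. The last two are upper limits, because 14.7 and 12 are ceilings.

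**3. Attempt to reproduce the power statement.** It cannot be reproduced without SD, alpha and power. I assumed 21 per arm (42 evaluable, with blocks of 2 or 4 implying 1:1), a two-sided 5% t-test and 80% power. That requires a standardised difference of 0.886, so the SD at 30 versus 21 events must be 9 / 0.886 = 10.2, a CV of 10.2 / 30 = 0.34.

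**4. Power at 12 per 8 hours under different readings of the variability.**

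- SD fixed at 10.2: 3.6 / 10.2 = 0.35, power 20%. The detectable relative reduction at 80% power is 9 / 12 = 75%. At the plan's own lower limit of 20, power is 46% and the detectable reduction 9 / 20 = 45%.
- SD proportional to the mean (CV 0.34): the standardised difference is still 0.886, so power stays at 80% and the detectable reduction at 30%.
- CV of the figure quoted in 6.4, reading 11.5 as an SD: 11.5 / 8.2 = 1.40. The standardised difference is 0.30 / 1.40 = 0.21 at any rate, so power is about 10% at 30, at 14.7 and at 12. For 80% power the relative reduction would have to be 0.886 × 1.40 = 1.24, above 100%, so no reduction qualifies.
- Count models, for comparison: a negative binomial calibrated to 80% at 30 (dispersion 0.13) gives 67% at 12. A pure Poisson model gives 95% at 12 and over 99.9% at 30.

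**The case against.** The best defence is that 20-30 is not a calculation error. It satisfies the discount rule for the 36-week rate, and 6.4 describes it as a baseline figure. Thirty-six weeks lies inside the entry window, is when BPD is formally diagnosed (section 5.2.1), and opens the primary-objective window. This stands: the 36-week rate can suit infants who enter near that age. The mismatch is with the second cited source and with the comparisons at 40 weeks and later.

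The source infants also differ. Section 1.3 says: "A recent trial of late caffeine therapy enrolled infants who were at least 33 PMA and in room air". This trial selects infants still on respiratory support at 36 weeks, who may have more IH. That stands too, but 6.4 claims no upward adjustment on this ground. If one was intended, it needs to be written down.

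A reader might infer that the plan's sources put the rate at 12-15 per 8 hours from 40 weeks on. They do not. The documents contain no rate at 40 weeks or later. The figure of 12 is a ceiling at 39 weeks. The figure of 14.7 is half of a median to which 6.4 attaches no age; section 1.3 describes that population from birth to at least 9-10 weeks of age. Where counts are skewed, half a median is not a ceiling on half the mean.

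The trial is a pilot, and section 6.3.2 concedes limited power. That concession is worded for the exploratory analyses, whereas IH incidence is a primary endpoint with its own power claim. Section 6.5 will review mean IH rates after 10 and 20 completers but attaches no sample-size rule to them.

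**Conclusion.** The concern holds in this form. By the plan's own rule, 20-30 events per 8 hours is supported by one of the two sources in 6.4 and not by the other, and the value used for power, 30, exceeds that other source's entire median. The rate that fits predates the first named IH comparison by about four weeks, and the protocol reports a 64% fall in the caffeine-trial control group between 35 and 39 weeks. At 12 per 8 hours, the 39-week ceiling, the 30% effect is 3.6 events instead of 9.

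A reader might go on to conclude that the lower rate cuts power to about 20%. The documents do not support that. The figure needs an SD back-solved from an assumed 80% power and held fixed while the mean falls. If the SD scales with the mean, nothing is lost; with the CV printed in 6.4, power is about 10% even at 30, so the rate hardly matters and the variance does. The defect is an unsupported planning range together with an unstated SD. All power figures assume 21 per arm and two-sided 5%, which 6.4 does not state.

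**What to change.** In section 6.4:

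- Label 30 events per 8 hours as a best case based on the 36-week rate.
- Replace 20-30 with a range that includes what the plan's inputs give, each tied to its source: under 32.8 at 36 weeks; under 14.7 from the Canadian Oxygen Trial median, not presented as a 39- or 40-week rate; under 12 at 39 weeks; unknown from 40 weeks on.
- If a higher rate is expected because the infants have BPD, say so and give the factor assumed.
- State the SD or overdispersion, alpha, sidedness and power behind the figure of 42.
- Restate the detectable reduction across that range, including at the CV of 1.40 implied by the quoted variability.

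The number enrolled should not change. The cost is a rewritten paragraph and a short sensitivity table, and the stated planning case will look less favourable. The blended IH rate reviewed at the interim looks would then have a benchmark that matches the plan's own sources.

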6.5 Interim Analysis

Interim analyses will be performed after 10 and 20 participants complete the study observation period (25% and 50%). The goal of the two interim analyses is to evaluate rates of drop-out, ensure that sufficient useable data are acquired, assess mean rates of IH across the entire population, and review accumulating safety data.

7 STUDY INTERVENTION

7.1 Description

We will randomize infants with moderate or severe BPD to lower (target SpO₂ of 90-94%) or higher SpO₂ target ranges (target SpO₂ of >=96%). The study team will then use novel technology to monitor infants starting at randomization, continuing after discharge and until 6 months corrected age, titrating supplemental oxygen to achieve these target SpO₂ ranges.

All trial participants will be provided with a study oximeter. Families will be instructed to use the study monitor continuously each night or when the baby is napping. The research monitor will stay in the child's sleep space and set with alarm limits of 79% and 101% and will be attached nightly when the infant is placed in the bed (in addition to the clinical monitor if prescribed). The research oximeter will be set for 2 second averaging and sampling. In addition, we will collect photoplethysmography (PPG) data at a rate not greater than 100 Hz to aid in identifying errors in the SpO₂, likely caused by motion artifact.

Infants enrolled in the current study who are discharged on home oxygen will be provided with standard clinical monitors by their home care companies, which will be set with alarm limits of 88% and 101%, and used with a frequency determined by the discharging clinician.

7.1.1 Treatment Compliance and Adherence

Data will be transmitted continuously from the home oximeter to the study team at CHOP. Data will then be reviewed weekly to ensure that families are using the device nightly as required per protocol, as well as to evaluate the integrity of transmitted data. If families are not using the monitor, the study team will contact them to facilitate adherence to the study protocol.

8 SAFETY MANAGEMENT

8.1 Clinical Adverse Events

Clinical adverse events (AEs) will be monitored throughout the study.

8.2 Adverse Event Reporting

The Investigator is responsible for recording and reporting unanticipated problems related to research that occur during and after study treatment. Unanticipated problems related to the research involving risks to subjects or others that occur during the course of this study (including SAEs) will be reported to the IRB in accordance with CHOP IRB SOP 408: Unanticipated Problems Involving Risks to Subjects. AEs that are not serious but that are notable and could involve risks to subjects will be summarized in narrative or other format and submitted to the IRB at the time of continuing review.

8.3 Definition of an Adverse Event

An adverse event is any untoward medical occurrence in a subject who has received an intervention (drug, biologic, or other intervention). The occurrence does not necessarily have to have a causal relationship with the treatment. An AE can therefore be any unfavorable or unintended sign

(including an abnormal laboratory finding, for example), symptom, or disease temporally associated with the use of a medicinal product, whether or not considered related to the medicinal product.

All AEs (including serious AEs) will be noted in the study records and on the case report form with a full description including the nature, date and time of onset, determination of non-serious versus serious, intensity (mild, moderate, severe), duration, causality, and outcome of the event.

8.4 Definition of a Serious Adverse Event (SAE)

Important medical events that may not result in death, be life-threatening, or require hospitalization may be considered a serious adverse event when, based upon appropriate medical judgment, they may jeopardize the subject and may require medical or surgical intervention to prevent one of the outcomes listed in this definition.

A distinction should be drawn between serious and severe AEs. A severe AE is a major event of its type. A severe AE does not necessarily need to be considered serious. For example, nausea which persists for several hours may be considered severe nausea, but would not be an SAE. On the other hand, a stroke that results in only a limited degree of disability may be considered a mild stroke, but would be an SAE.

8.4.1 Relationship of SAE to intervention

The relationship of each SAE to the study intervention should be characterized using one of the following terms in accordance with CHOP IRB Guidelines: definitely, probably, possibly, unlikely or unrelated.

8.5 IRB/IEC Notification of SAEs and Other Unanticipated Problems

The Investigator will promptly notify the IRB of all on-site unanticipated, serious Adverse Events that are related to the research activity. Other unanticipated problems related to the research involving risk to subjects or others will also be reported promptly. Written reports will be filed using the eIRB system and in accordance with the timeline below. External SAEs that are both unexpected and related to the study intervention will be reported promptly after the investigator receives the report.

Type of Unanticipated Problem	Initial Notification (Phone, Email, Fax)	Written Report
Internal (on-site) SAEs Death or Life Threatening	24 hours	Within 2 calendar days
Internal (on-site) SAEs All other SAEs	7 days	Within 7 business days
Unanticipated Problems Related to Research	7 days	Within 7 business days
All other AEs	N/A	Brief Summary of important AEs may be reported at time of continuing review

8.5.1 Follow-up report

If an SAE has not resolved at the time of the initial report and new information arises that changes the investigator's assessment of the event, a follow-up report including all relevant new or reassessed information (e.g., concomitant medication, medical history) should be submitted to the IRB. The investigator is responsible for ensuring that all SAE are followed until either resolved or stable.

8.6 Medical Emergencies

It is possible that a home monitor will alarm repeatedly for low saturations. In this case, the family will be instructed to contact the child's doctor and if necessary bring the child to the emergency room. Such events will be monitored closely and reported to the IRB as necessary according to the above guidelines about adverse event reporting.

9 STUDY ADMINISTRATION

9.1 Treatment Assignment Methods

9.1.1 Randomization

The plan for randomization is described above in section 3.2.

9.1.2 Blinding

The plan for allocation concealment is described above in section 3.2. Given the nature of the intervention to be evaluated participants and research staff will not be blinded to group assignment.

9.2 Data Collection and Management

The proposed research will be carried out using, in part, computing facilities available at the PRECISE (Penn Research in Embedded Computing and Integrated Systems Engineering) Center at the University of Pennsylvania. The PRECISE center has a large dedicated facility for embedded system development and prototyping with an array of electronic measurement and instrumentation equipment.

The oximeters each have a port into which a small computer/dongle designed for this study is plugged. The dongle contains a wi-fi device ("hot spots") that will transmit the data continuously. The dongle can store data in the case of dropped wi-fi signal. We will transmit SpO2 data and pulse rate, along with some data that indicate the quality of the signal, but not the waveforms. Only oximeters on loan from Masimo will be used for this study. In addition only cellular modems provided by CHOP will be used for this study.

The lab provides secure storage in addition to the hardware and computing resources necessary to maintain a large-scale monitoring system. The PRECISE center has developed the device that will transmit data from the Masimo monitor to the study team at CHOP wirelessly. They will maintain these devices and the data transmission throughout the study. This team will not have access to patient identifiers; data streams will be labeled only with study ID numbers. However, the data streams will be date and time stamped, which is essential in order to ensure data integrity. PRECISE will then strip dates and may perform analyses on de-identified and coded data set with dates

removed, therefore they will not be considered engaged in human subject's research nor is there a need for a data sharing agreement.

As mentioned, data may be managed and stored in a password-protected database using the research-focused electronic web-based data capture system REDCap (Research Electronic Data Capture). REDCap is a secure software solution and workflow methodology for supporting clinical research databases developed by the informatics core at Vanderbilt University. Automated time-stamped backup files are made daily from the replicated database by CHOP Research Information Systems. Backup files are encrypted and transferred to the secure CHOP Research Information Systems Storage Area Network (SAN) accessible only to designated personnel. REDCap provides automated export procedures for seamless data downloads to Excel and commonly-used statistical packages. The database will incorporate range and consistency checks to ensure quality control and will signal the presence of questionable items. Only study team members will have access to the REDCap database for data entry under the supervision of and after training by the PI. Hard copies of data instruments will be stored in a locked cabinet in a locked office in the Division of Neonatology at CHOP.

To maintain confidentiality, participants will be assigned a unique identifier that contains no protected health information. All source documents will have the study identifier only. Access to the identifiers of the coded data will be controlled by the PI and only study team members will have access to the electronic and paper data.

Individuals who withdraw from the study after enrollment will be removed from the main study database (s) and placed in to a separate encrypted, password-protected database maintained at CHOP. This file will be deleted at the end of the study. Records will be retained in compliance with CHOP Policy A-3-9

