4.6.1 Early Termination Study Visit

Subjects who withdraw from the study will be asked to notify the study team of their decision. If participants indicate that they do not want us to collect, use, or share their health information any longer, we will ask them to inform a research team member or the Principal Investigator, [name].

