5.1.2 Inpatient Data Collection

After enrollment and randomization, the following data will be collected from the EMR while the patient is in the hospital:

- Birthweight
- Birth hospital
- Date of transfer to CHOP,HUP, of PAH (if applicable)
- Antenatal steroid treatment
- Reason for preterm birth
- Respiratory support
- Growth parameters at 36 weeks PMA
- Growth parameters at 40 weeks PMA
- Treatment with the following medications for BPD: iNO, postnatal steroids, inhaled bronchodilators, inhaled steroids, other
- Any surgeries
- Neonatal morbidities (surgical NEC, PDA ligation, ROP surgery, etc).
- Screening for pulmonary hypertension

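### Section 9.2 removes withdrawn infants from the main database and later deletes their file, with no stated route into the all-randomized primary or all-entered safety analysis

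*Combined protocol and SAP*

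**What the plan says.** Section 9.2 (Data Collection and Management) sets a rule for families who leave: "Individuals who withdraw from the study after enrollment will be removed from the main study database (s". Their records are "placed in to a separate encrypted, password-protected database maintained at CHOP". On what happens to those records it says "This file will be deleted at the end of the study", and the next sentence reads "Records will be retained in compliance with CHOP Policy A-3-9".

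The statistical section defines the analysis sets without exception. Section 6.3.2 makes the primary analysis intention to treat, covering every randomized infant. Section 6.3.3 puts every infant entered into the safety analysis.

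Section 4.6 allows families to withdraw at any time. It separately allows the investigator to discontinue an infant for poor adherence or intolerance of testing, and it says that missed appointments are not a reason for withdrawal. Section 4.6.1 asks families who withdraw to notify the team, and then describes a further case: "If participants indicate that they do not want us to collect, use, or share their health information any longer".

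**The concern.** Under intention to treat, an infant who leaves early still belongs to the assigned arm, and whatever was measured before departure still counts. Section 9.2 takes those infants out of the database from which an analyst would naturally work. It does so for everyone who withdraws, including families who only stop the nightly monitoring and would be content for earlier data to be used.

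What is at stake is the make-up of the primary and safety sets. Section 9.1.2 confirms that families and research staff know the assignment, so the decision to leave may be related to arm or to how the infant is doing. If those infants drop out of the dataset, the comparison is between infants whose families stayed. Intermittent hypoxemia, growth and adverse-event data already collected would go unused. The generalized estimating equations planned in 6.3.2 can accept infants with incomplete follow-up, so the data before withdrawal are usable.

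**Working it through.** The point is one of text. The plan gives no withdrawal rate and no figure to reproduce, so the check sets the sections side by side.

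1. **Who is removed.** Section 9.2 covers individuals who withdraw after enrollment, with no condition on reason or on permission to keep data. Section 4.6.1 treats refusal of further collection, use or sharing as an additional indication. Section 9.2 does not use that distinction.
2. **Who must be analysed.** Section 6.3.2 requires all randomized infants and 6.3.3 requires all entered. Withdrawn infants belong to both sets.
3. **Is there a bridge?** No section says that the separate file is merged with, or analysed alongside, the main database. No section gives a method for outcomes missing after withdrawal.
4. **When is the file deleted?** At the end of the study, which 9.2 does not define relative to the final analysis. Section 4.3.3, which carries End of Study as its title, concerns the child reaching 6 months corrected age and says nothing about analysis.
5. **Consequence.** An analysis of the main database alone meets neither 6.3.2 nor 6.3.3. An analysis of both files before deletion could meet both, but that step is unwritten.
6. **What else survives?** Section 9.2 mentions hard copies and says "Automated time-stamped backup files are made daily from the replicated database by CHOP Research Information Systems". The computing center handles the oximetry streams: "PRECISE will then strip dates and may perform analyses on de-identified and coded data set with dates" removed. For the inpatient phase, 5.1.2 says "the following data will be collected from the EMR while the patient is in the hospital". Section 4.6 sends serious, related events learned of after withdrawal to the source documents and case report form. None of these is described as a way of returning a withdrawn infant to an analysis set.

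**Scale.** The only nearby figure is in 3.3.2: up to 50 enrolled to obtain 42 evaluable. The allowance is 50 − 42 = 8 infants, and 8/50 = 16%. If withdrawals ran from 0 to 8, the main database would hold 50 to 42 of 50 randomized infants, that is 100% to 42/50 = 84%. The allowance covers non-evaluable data from any cause. It is not a withdrawal rate, and the range is an illustration only.

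**The case against.** The best reply is that 9.2 is a storage paragraph and excludes nobody from an analysis. Section 6 names the analysis sets outright, the separate file exists until the study ends, and an analyst who follows Section 6 would open both files. That reading is possible, so a reader who infers that the plan forbids an intention-to-treat analysis goes too far. The reply does not remove the problem. Section 9.2 gives a positive instruction to remove and then delete, and compliance with 6.3.2 and 6.3.3 rests on a step that nobody has been told to take.

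A second reply is that information survives elsewhere. This stands in part. A reader might infer that the data are lost for good, but the copies listed above mean that permanent loss is not established. Safety information in particular does not rest on the main database alone: besides 4.6, Section 8 provides for reporting of serious events to the IRB and their follow-up until resolved or stable. These routes do not cover non-serious or unrelated events in an analysable form, nor oximetry and growth data from before withdrawal.

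A third reply is that the consent and HIPAA form (9.6) or the cited retention policy may settle the matter. Neither text was available. Either could bear on the remedy, but retaining a record is not the same as including it in an analysis.

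A reader might also infer that the interim reviews in 6.5 would miss these infants. The documents do not support that: 6.5 does not confine the review to the main database, and a separate file of withdrawn infants itself identifies drop-outs.

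**Conclusion.** The concern holds as an inconsistency that should be fixed. As written, 9.2 removes all infants whose families withdraw and later deletes their file, and the plan states no route by which they enter the analyses that 6.3.2 and 6.3.3 promise.

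The practical effect cannot be sized. Withdrawals may be zero, and the 16% allowance is a planning figure for any cause. A reader might infer that the trial's comparison will be biased. The documents support only that it could be: unblinded assignment makes informative withdrawal plausible, but nothing fixes its frequency, its split between arms, or the size or direction of any bias. It is also unclear whether infants discontinued by the investigator under 4.6 count as having withdrawn for the purposes of 9.2.

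The conclusion assumes that the main study database is the source for analysis unless the plan says otherwise, and that the unseen consent form and policy do not already supply the missing route.

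**What to change.** Rewrite 9.2 along these lines:

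- Coded data collected up to withdrawal stay in the analysis dataset with assigned arm, date and reason for withdrawal, and enter the intention-to-treat and safety analyses.
- Data already collected are excluded only where a family revokes their use and the consent/HIPAA terms or applicable rules require removal. The number so excluded is reported by arm.
- The text states whether infants discontinued by the investigator are covered.
- The deletion sentence is removed or reconciled with the retention sentence, after checking the consent form and the cited policy.

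This keeps data already in hand. It does not remove bias from outcomes missing after withdrawal, for which the plan names no method.

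The cost is a wording amendment and a check of two documents. If the consent form promises removal or deletion, it may need amending too, and families already enrolled may remain under the terms they signed. Sample size, study procedures and patient burden do not change. The amendment is best made before any file is deleted.
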